2.1. Study Rationale

Residual cardiovascular risk is still high, despite the current standard of care that includes maximally tolerated statin. Studies show that a reduction in circulating biomarkers, such as non-HDL-C and ApoB, are associated with a reduction in MACE (Bowman et al. 2017; Ference et al. 2019).

This study aims to investigate the impact of LY3561774 on surrogate biomarkers of MACE in participants with mixed dyslipidemia. This is the first Phase 2 study and data from this study will inform dose decisions for the clinical development of LY3561774.

2.2. Background

A detailed description of the chemistry, pharmacology, efficacy, and safety of LY3561774 is provided in the IB.

Clinical Study EZCA preliminary results

Study J3F-MC-EZCA (EZCA) is a first-in-human study of LY3561774, assessing the safety, tolerability, PK, and PD of single-ascending subcutaneous and repeat subcutaneous doses of LY3561774 in participants with dyslipidemia. The study had 3 parts that are described in this table.

Study EZCA Part	Subcutaneous dosing frequency	Dose levels	Number of participants at data cut-off date for preliminary results
A	Single	24, 72, 208, 480 and 960 mg	40
B	2 doses given 28 days apart	208 or 480 mg	16
C	Single	208 or 480 mg	18 Japanese participants ^a

^a Part C was a cohort of only Japanese participants.

Safety

Preliminary results suggest LY3561774 is generally well tolerated when administered as single doses up to 960 mg and as 2 doses of either 208 or 480 mg.

Treatment emergent adverse events were mostly mild in severity.

Part A

Treatment emergent adverse events reported by at least 2 participants included headache, increased blood creatine phosphokinase, and rash.

After single doses, transient elevations of liver enzymes (AST or ALT >2x ULN) and/or creatine kinase (>5x ULN) were observed. These were not associated with any clinical signs or symptoms.

All ISRs resolved spontaneously and there was no apparent relationship of the frequency or severity with the dose.

Part B

Treatment emergent adverse events reported by at least 2 participants included headache, increased hepatic enzymes, and rash.

No clinically relevant changes in laboratory values were observed.

Injection-site reactions were reported after administration of 1 dose or repeat dosing, and they spontaneously resolved with no apparent relationship to dose.

Part C

Treatment emergent adverse events reported by at least 2 participants included ecchymosis.

One participant had ALT >2x ULN, but less than 3x ULN with no associated clinical signs or symptoms.

Injection-site reactions were reported by 4 participants.

Pharmacokinetics

Part A

After single doses, LY3561774 PK across the tested dose range exhibited

- linear PK
- median t_{max} between 7.5 and 12.5 hours, and
- mean terminal half-life from 5.5 to 12.9 hours.

Part B

After 2 doses, LY3561774 PK exhibited

- approximate dose proportionality across the dose range tested
- consistent PK with single-ascending dose cohorts
- median t_{max} between 9 and 16 hours after the first dose
- median t_{max} between 9 and 10.5 hours after the 2nd dose on Day 29, and

- a mean $t_{1/2}$ of approximately 7 hours.

Pharmacodynamics

Dose-dependent decreases in ANGPTL3, TG, and LDL-C were observed after single doses and 2 doses across the tested dose range. The duration of effect continued up to the last collection time point after dosing at Day 169.

2.3. Benefit/Risk Assessment

Detailed information about the known and expected benefits and risks and reasonably expected AEs of LY3561774 may be found in the IB.

2.3.1. Risk Assessment

Study EZCA clinical data

Preliminary results from Study EZCA in healthy participants suggest LY3561774 is generally well tolerated (See Section 2.2).

Nonclinical data

Based on the nonclinical data, LY3561774 is not considered to be a high-risk compound.

Potential risks

Based on the current clinical data, nonclinical safety pharmacology and toxicology studies, and considering the oligonucleotide class effects, potential risks for clinical study participants receiving LY3561774 are hepatobiliary events, systemic allergic or hypersensitivity reactions, or ISRs.

Mitigations for potential risks

Liver enzyme levels will be monitored at multiple time points and clinical events will be monitored closely throughout the study. Participants will also have 2 MRI scans to determine change in hepatic fat fraction (see Section 8.2.4).

Hypersensitivity reactions will be managed per Section 8.3.3.

Injection-site reaction assessments will occur throughout the study.

2.3.2. Benefit Assessment

The efficacy of LY3561774 for lowering lipids has not been established. Participants may benefit by receiving personal health information from the physical examinations and from other routine safety assessments performed in this study.

2.3.3. Overall Benefit Risk Conclusion

Considering the measures taken to minimize risk for the participants in this study, the potential risks identified in association with LY3561774 are justified by the anticipated benefits that may be afforded to participants with mixed dyslipidemia.

3. Objectives, Endpoints, and Estimands

Objectives	Endpoints
Primary	
To evaluate if LY3561774 is superior to placebo for the treatment of mixed dyslipidemia in adults.	Percent change from baseline at Day 180 for ApoB.
Secondary	
Compare the clinical response of LY3561774 to placebo.	Percent change from baseline at Day 180 for 
 • ANGPTL3 • LDL-C • HDL-C • Non-HDL-C, and • Triglycerides.
	Percent change from baseline at Day 270 for 
 • ANGPTL3 • Non-HDL-C • LDL-C • HDL-C • ApoB, and • Triglycerides.
Characterize the pharmacokinetics (PK) of LY3561774.	Plasma concentrations of LY3561774.
Compare the effect of LY3561774 to placebo on safety endpoints.	Frequency of treatment-emergent adverse events.
To describe the safety of LY3561774 in participants with mixed dyslipidemia	Summary of safety data, including number and incidence of 
 • TEAEs • SAEs, and • discontinuations due to AEs.
Exploratory	
Assess the relationship between LY3561774 dose and clinical endpoints and potential participant factors that may influence these relationships.	Dose-response analyses for key efficacy and safety parameters.

Objectives	Endpoints
Assess the relationship between LY3561774 exposure and clinical endpoints and potential participant factors that may influence these relationships.	Exposure-response analyses for key efficacy and safety parameters.
Evaluation of immunogenicity.	Incidence of treatment-emergent anti-drug antibodies (ADA).
Compare the effect of LY3561774 to placebo on clinical endpoints or biomarkers.	Percent change from baseline at Day 180 for 
 • hsCRP • ApoA-I • ApoC-III • VLDL-C • UACR • HbA1c, and • FG.
Compare the effect of LY3561774 to placebo for key efficacy parameters.	Absolute change from baseline at Day 180 for 
 • Non-HDL-C • LDL-C • HDL-C • ApoB, and • Triglycerides.
Compare the effect of LY3561774 to placebo on hepatic fat fraction.	Change from baseline for MRI hepatic fat fraction at Day 180.

Abbreviations: AE = adverse event; ANGPTL3 = angiopoietin-like protein 3; Apo = apolipoprotein; FG = fasting glucose; HbA1c = hemoglobin A1c; HDL-C = high-density lipoprotein-cholesterol; hsCRP = high-sensitivity C-reactive protein; LDL-C = low-density lipoprotein-cholesterol; MRI = magnetic resonance imaging; SAE = serious adverse event; TEAE = treatment emergent adverse event; UACR = urinary albumin/creatinine ratio; and VLDL-C = very-low-density lipoprotein-cholesterol.

Primary estimand

The primary clinical question of interest is

What is the treatment difference in ApoB percent change from baseline after 180 days of treatment in participants who meet the inclusion criteria and would have completed the treatment period?

Efficacy estimand attributes

This table describes the efficacy estimand attributes.

Efficacy Estimand Attribute	Description
Population	Participants who meet the inclusion criteria. Further details can be found in Sections 5 and 9.
Endpoint	Percent change from baseline in ApoB at Day 180.
Treatment condition	The randomized treatment.
Population-level summary	Difference in mean percent changes in ApoB at Day 180 between LY3561774 and placebo.

Intercurrent events

The intercurrent events including the following are handled by the hypothetical strategy:

- Permanent discontinuation of intervention.
- Initiation of excluded medications taken during the study.
- New initiation of any lipid-lowering drug required to be on a stable regimen prior to treatment per the protocol inclusion criteria.

The potential outcome of interest is the response in the efficacy measurement if participants adhere to the randomized treatment.

Rationale for the efficacy estimand

This Phase 2 study aims to study the efficacy of LY3561774 under the ideal condition that all participants adhere to the randomized treatment.

Estimand(s) for secondary objectives

The same estimand for the primary objective will be used for the secondary clinical response endpoints.

Unless specified otherwise, safety assessments will be guided by an estimand comparing safety of LY3561774 doses with placebo irrespective of adherence to study intervention, including data collected during the treatment period and safety follow-up.

4. Study Design

4.1. Overall Design

This is a Phase 2, randomized, double-blind, placebo-controlled, parallel-arm study to investigate the efficacy and safety of LY3561774 in adults with mixed dyslipidemia.

The planned treatment arms are

- 100 mg LY3561774 or placebo
- 400 mg LY3561774 or placebo, and
- 800 mg LY3561774 or placebo.

Intervention administration is by subcutaneous injection.

Dosing will occur twice during the study, on Day 0 and Day 90 (-5 to +10 days).

4.1.1. Design Outline

Screening

Interested participants will sign the appropriate informed consent document(s) prior to completion of any procedures.

The investigator will review symptoms, risk factors, medical history, concomitant medications and other inclusion and exclusion criteria prior to any diagnostic procedures. If the participant is eligible after this review, then the site will perform the diagnostic procedures to confirm eligibility.

Double-blind treatment and assessment period

This is the general flow during the treatment and assessment period:

- Complete MRI at any date prior to randomization
- Complete baseline procedures and sample collection
- Participants are randomly assigned to an intervention group, and
- Participants complete all visit procedures including efficacy assessments, safety monitoring, study intervention dosing, and post-dosing sample collection.

Safety follow-up

If a participant's ApoB levels do not return to $\geq 80\%$ of baseline on Day 270, then they will continue to the follow-up visit at Day 360.

If a participant's ApoB levels return to $\geq 80\%$ of baseline on Day 270, then Day 270 is their last study visit.

4.2. Scientific Rationale for Study Design

Primary endpoint

The primary endpoint, ApoB, is considered the strongest surrogate biomarker and predictor of future cardiovascular events. Plasma ApoB levels reflect the number of circulating atherogenic ApoB-containing lipoproteins, namely VLDL, intermediate-density lipoprotein, remnants of TG-rich lipoproteins, LDL, and lipoprotein(a).

The clinical benefit of lowering both TG and LDL-C levels in patients with mixed dyslipidemia appears to be proportional to the absolute change in ApoB (FERENCE et al. 2019). Even though LDL-C and non-HDL-C are good predictors of cardiovascular risk (Puri et al. 2016), more recent studies suggest that ApoB may be the primary driver of atherosclerosis and that lowering the concentration of all ApoB-containing lipoproteins should be the focus of therapeutic strategies (FERENCE et al. 2020; Richardson et al. 2020; Sniderman et al. 2019; Marston et al. 2022).

Overall design

The 270-day duration of the treatment period is based on the demonstrated efficacy and prolonged activity of the intervention in the Phase 1 Study EZCA. This duration is also a reasonable timeframe to observe efficacy for the treatment of mixed dyslipidemia, which will inform the dose level and frequency in future clinical studies.

The follow-up visit after the last dose is designed to capture any additional safety signals and to quantitate the return to baseline for ApoB.

Placebo is chosen as the control treatment to assess whether any observed effects are treatment related or simply reflect the study conditions. The double-blind design minimizes bias on safety assessments and allows a more robust comparison among LY3561774 doses and placebo.

In this study, collection of demographic information includes ethnicity and race. The scientific rationale is based on the need to assess variable response in safety and/or efficacy based on race or ethnicity. This question can be answered only if all the relevant data are collected.

4.3. Justification for Dose

Planned dose levels and frequency for this study

In this study, the planned subcutaneous doses of 100 mg, 400 mg, and 800 mg will evaluate the effect of LY3561774 in participants with mixed dyslipidemia. Dosing will occur twice during the study approximately 90 days apart.

Justification for dose levels and frequency

The doses and frequency were selected based on human safety, tolerability, PK and PD from Phase 1 evaluations, and nonclinical toxicology. Detailed information on these studies may be found in the IB.

The selected dose levels and dosing frequency with prolonged post-dose evaluations of ApoB will support a robust dose-exposure-response analysis of multiple safety and efficacy measures.

Data from this study will support future clinical development of LY3561774.

Phase 1 clinical Study EZCA

The available clinical safety data from healthy participants after receiving LY3561774 treatment up to 960 mg supports continued clinical development in Phase 2.

LY3561774 treatment up to 960 mg appears to reduce ANGPTL3 and TG levels dose-dependently.

Based on a PK/PD model of Study EZCA interim data, the 800 mg dose given every 90 days is expected to provide optimal ApoB and non-HDL-C reduction. The 100 mg dose given every 90 days is chosen as a low efficacy dose to optimize dose-exposure-response analysis.

Nonclinical toxicology data

The margin of safety for the 800 mg maximum dose in this study is expected to have an exposure multiple of approximately 9.6 times the NOAEL level based on the 6-month, repeat-dose mouse toxicity study and 22 times the NOAEL based on the 9-month, repeat-dose monkey toxicity study.

4.4. End of Study Definition

The end of the study is defined as the date of last scheduled procedure shown in the SoA (Section 1.3) for the last participant in the trial globally.

A participant is considered to have completed the study if the participant completes all applicable scheduled procedures as shown in the SoA (Section 1.3).

5. Study Population

Prospective approval of protocol deviations to recruitment and enrollment criteria, also known as protocol waivers or exemptions, is not permitted.

5.1. Inclusion Criteria

Participants are eligible to be included in the study only if all of the following criteria apply:

Age

1. Must be 18 years of age or older at the time of signing the informed consent.

Type of participant and disease characteristics

2. Have fasting TGs within the range of 150 to 499 mg/dL (1.69 to 5.64 mmol/L) at screening.
3. Have fasting LDL-C \geq 70 mg/dL (1.81 mmol/L) at screening.
51. Have fasting non-HDL-C \geq 130 mg/dL (3.36 mmol/L) at screening.
4. Must be on a stable moderate or high-intensity dose of a statin (See Section 10.7.1) for at least 2 months before screening and remain on the same medication and dose for the duration of the study.

Weight

5. Have a body mass index within the range of 18.5 to 40.0 kg/m², inclusive.

Sex and contraceptive/barrier requirements

6. Are WOCBP who agree to use contraception as outlined in Section 10.4 or
Are WNOCBP as defined in Section 10.4 or
Are men who agree to use contraception as outlined in Section 10.4.

Contraceptive use by participants should be consistent with local regulations regarding the methods of contraception for those participating in clinical studies.

Definitions and contraception requirements for participants in this study are provided in Section 10.4.

Informed consent

7. Are capable of giving signed informed consent as described in Section 10.1.3, which includes compliance with the requirements and restrictions listed in the ICF and in this protocol.

Other inclusions

8. Have not started a structured weight loss program within 3 months of screening, or plan on starting a program during the study.
9. If taking hypertensive therapy, doses must be stable 30 days prior to screening.
10. Are reliable and willing to make themselves available for the duration of the study and are willing to follow study procedures.
11. Have an optimal MRI image quality at screening, as assessed by central laboratory.

5.2. Exclusion Criteria

Participants are excluded from the study if any of the following criteria apply:

Diabetes and cardiovascular medical conditions

12. Have, in the 6 months prior to screening, uncontrolled Type 1 or Type 2 diabetes, defined as an episode of ketoacidosis or hyperosmolar state requiring hospitalization, or have an HbA1c $\geq 8\%$ at screening.
13. Have a history of nephrotic syndrome.
14. Have had within the past 3 months prior to screening
 - a. Myocardial infarction
 - b. Unstable angina
 - c. Coronary artery bypass graft
 - d. Percutaneous coronary intervention – diagnostic angiograms are permitted
 - e. Peripheral artery disease
 - f. Transient ischemic attack, or
 - g. Cerebrovascular accident.
15. Have New York Heart Association Class III or IV heart failure or last known left ventricular ejection fraction $< 30\%$.
16. Have undergone LDL apheresis within 12 months prior to screening.

Other medical conditions

17. Have a TSH outside of the 0.4 to 6.0 mIU/L range.
18. Have a history or presence of an underlying disease, or surgical, physical, or medical condition that, in the opinion of the investigator would potentially affect participant safety within the study or interfere with the interpretation of data.
19. Have, within 1 year prior to screening or plan on having during the study, surgical treatment for obesity.
20. Have within 5 years prior to screening a history of an active or untreated malignancy or are in remission from a clinically significant malignancy.

Exceptions:

- Basal or squamous cell skin cancer.
 - Cervical carcinoma in situ or prostate cancer in situ.
21. Have a history of or current significant psychiatric disorders considered clinically significant in the opinion of the investigator.
 22. Have within 3 years prior to screening a history of chronic alcohol abuse, IV drug abuse, or other illicit drug abuse.
 23. Have within 3 months prior to screening used marijuana or tetrahydrocannabinol containing products or are unwilling to abstain from use during the study.
 24. Have 2 or more clinically significant or severe drug allergies, or severe post-treatment hypersensitivity reactions, including, but not limited to
 - a. erythema multiforme major
 - b. linear immunoglobulin A dermatosis
 - c. toxic epidermal necrolysis, or

- d. exfoliative dermatitis.
- 25. Have a history of acute or chronic pancreatitis.
- 26. Have active severe liver diseases, such as cirrhosis, active hepatitis, or biliary obstruction with hyperbilirubinemia.
- 27. Have a history of infection within 14 days before screening that, in the opinion of the investigator, would potentially affect participant safety within the study or interfere with the interpretation of data.
- 28. Have HIV infection or are positive for HIV antibodies.
- 29. Have current infection with hepatitis B virus or positive for hepatitis B surface antigen.
- 30. Have a current infection with hepatitis C virus or positive hepatitis C virus antibody.

Diagnostic assessments

- 31. Have clinically relevant anemia, as defined by the investigator.
- 32. Have laboratory values, in relation to the reference range,
 - ALT >3.0X ULN or
 - ALP >1.5X ULN or
 - TBL >1.5X ULN, except for participants diagnosed with Gilbert's syndrome.
- 33. Have an eGFR <30 mL/min/1.73 m².
- 34. Have a pulse rate >100 bpm, a repeat measure is allowed.
- 35. Have uncontrolled hypertension with a resting blood pressure ≥180 mm Hg systolic and/or ≥100 mm Hg diastolic, a repeat measure is allowed.

Prior/concomitant therapy

- 36. Have used or are taking products for the purpose of lowering lipid levels. This includes lipid-regulating medication, over-the-counter products, or herbal therapies.
See Section 10.7.3 for details on prohibited treatments and the timeframe relative to screening.
Exceptions: Statins, PCSK9 inhibitors, bempedoic acid, and ezetimibe.
- 37. Have within 3 months of screening, initiated treatment with SERMs, estrogens, progestins, testosterone, or thyroid hormone therapy.
- 38. Have or are currently taking HIV protease inhibitors, cyclophosphamide, or systemic retinoids.
- 39. Have within 6 months of screening had treatment with any oligonucleotide, including small interfering ribonucleic acid.
Exception: mRNA vaccines.
- 40. Have within 3 months of screening treatment with systemic corticosteroids, cyclosporine, isotretinoin, or anabolic agents.
Exceptions: local, topical, intra-articular, inhalation, or nasal corticosteroids.
- 41. Have within 1 month prior to screening treatment with
 - a. warfarin or other coumarins
 - b. direct thrombin inhibitors
 - c. Factor Xa inhibitors, or

- d. Heparins or heparinoids.
42. Are currently using a medication associated with weight gain or weight loss.
Exception: if the participant is on a stable dose for at least 3 months prior to screening and will continue the stable dose during the study.

Prior or concurrent clinical study experience

43. Are currently enrolled or have participated within the last 6 months in a clinical study involving an investigational intervention or any other type of medical research judged not to be scientifically or medically compatible with this study.
44. Have previously completed or withdrawn from this study.

Other exclusions

45. Are breastfeeding.
46. Have an average weekly alcohol intake more than 21 units per week for men and 14 units per week for women or are unwilling to stop alcohol consumption from 48 hours prior to each visit.
1 unit of alcohol is equal to
- 12 ounces or 360 mL of beer
 - 5 ounces or 150 mL of wine, or
 - 1.5 ounces or 45 mL of distilled spirits.
47. Are unwilling to have an MRI scan or have contraindications for MRI scanning
- a. have a cardiac pacemaker or implants made out of metal, for example, cochlea implants, nerve stimulators, magnetic vascular clips, or metallic heart valves
 - b. Have extreme claustrophobia
 - c. Weight or girth exceeds scanner capabilities, or
 - d. In the opinion of the investigator, have any condition or circumstance that would interfere with completion of the MRI.
48. Are Lilly employees or are employees of any third party involved in the study who require exclusion of their employees.
49. Are investigator site personnel directly affiliated with this study and/or their immediate families. Immediate family is defined as a spouse, parent, child, or sibling, whether biological or legally adopted.
50. Are unsuitable for inclusion in the study in the opinion of the investigator.

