7.1.1. Liver Chemistry Stopping Criteria

The study intervention should be interrupted or discontinued if 1 or more of these conditions occur.

Elevation	Exception
ALT or AST >8x ULN	
ALT or AST >5x ULN for more than 2 weeks	
ALT or AST >3x ULN and either TBL >2x ULN or INR >1.5	In participants with Gilbert's syndrome, doubling of direct bilirubin should be used for intervention interruption or discontinuation decisions rather than TBL >2x ULN.
ALT or AST >3x ULN with the appearance of fatigue, nausea, vomiting, right upper quadrant pain or tenderness, fever, rash, and/or eosinophilia (>5%)	
ALP >3x ULN, when the source of increased ALP is the liver	
ALP >2.5x ULN and TBL > 2x ULN	In participants with Gilbert's syndrome, doubling of direct bilirubin should be used for intervention interruption or discontinuation decisions rather than TBL >2x ULN.

ALP >2.5x ULN with the appearance of fatigue, nausea, vomiting, right upper quadrant pain or tenderness, fever, rash, and/or eosinophilia (>5%)	
---	--

Resumption of the study intervention can be considered only in consultation with the Lilly-designated medical monitor and only if the liver test results return to baseline and if a self-limited, non-intervention etiology is identified.

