10.2. Appendix 2: Clinical Laboratory Tests

The tests detailed in the table below will be performed by the Lilly-designated laboratory or by the local laboratory as specified in the table below.

In circumstances where the sponsor approves local laboratory testing in lieu of Lilly-designated laboratory testing, the local laboratory must be qualified in accordance with applicable local regulations.

Protocol-specific requirements for inclusion or exclusion of participants are detailed in Section 5 of the protocol.

Additional tests may be performed at any time during the study as determined necessary by the investigator or required by local regulations.

Investigators must document their review of the laboratory safety results.

Laboratory results that could unblind the study will not be reported to investigative sites or other blinded personnel.

Clinical Laboratory Tests	Comments
Hematology	Assayed by Lilly-designated laboratory.
Hemoglobin	
Hematocrit	
Erythrocyte count (RBCs - red blood cells)	
Mean cell volume	
Mean cell hemoglobin	
Mean cell hemoglobin concentration	
Leukocytes (WBCs - white blood cells)	
Differential	
Percent and Absolute Count of:	
Neutrophils, segmented	
Bands	
Lymphocytes	
Monocytes	
Eosinophils	
Basophils	
Platelets	
Cell morphology (RBC and WBC)	
Clinical Chemistry	Assayed by Lilly-designated laboratory.
Sodium	
Potassium	
Chloride	
Bicarbonate	
Total bilirubin	
Direct bilirubin	
Alkaline phosphatase (ALP)	
Alanine aminotransferase (ALT)	
Aspartate aminotransferase (AST)	
Gamma-glutamyl transferase (GGT)	
Blood urea nitrogen (BUN)	
Creatinine	
Creatine kinase (CK)	
Uric acid	
Total protein	
Albumin	
Calcium	
Phosphorus	
Glucose	
Amylase	
Lipase	
LDH	
Lipid Panel	Assayed by Lilly-designated laboratory.

Clinical Laboratory Tests	Comments
	After randomization, results will not be provided to investigative sites.
High-density lipoprotein cholesterol (HDL-C)	
Non-HDL-C	
Low-density lipoprotein cholesterol (LDL-C) direct	
Very-low-density lipoprotein cholesterol (VLDL-C)	
Cholesterol	
Triglycerides	
Coagulation Panel	Assayed by Lilly-designated laboratory.
PT-INR	
aPTT	
Urinalysis	Assayed by Lilly-designated laboratory.
Specific gravity	
pH	
Protein	
Glucose	
Ketones	
Bilirubin	
Urobilinogen	
Blood	
Nitrite	
Urine leukocyte esterase	
Microscopic examination of sediment	
Hormones (female)	
Follicle-stimulating hormone (FSH)	Assayed by Lilly-designated laboratory.
Urine pregnancy	Local laboratory.

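### Criterion 32 caps ALT, ALP and bilirubin at screening but not AST, so first-dose eligibility with a high AST rests on judgment and the AST repeat-test trigger can lie above the stopping limit

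*Protocol*

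**What the plan says.** **Entry.** Protocol 5.2, criterion 32, opens with "ALT >3.0X ULN or" and adds ALP above 1.5x ULN and total bilirubin above 1.5x ULN (Gilbert's syndrome exempt). No other inclusion or exclusion criterion gives a number for AST. AST belongs to the clinical chemistry panel (Protocol 10.2), which the Schedule of Activities (1.3) places at Visit 1 and every later visit.

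**Stopping.** Protocol 7.1.1 states: "The study intervention should be interrupted or discontinued if 1 or more of these conditions occur". The four transaminase conditions are:

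- "ALT or AST >8x ULN", with no further requirement
- either enzyme above 5x ULN, if this lasts beyond 2 weeks
- "ALT or AST >3x ULN and either TBL >2x ULN or INR >1.5" (a separate bilirubin rule covers Gilbert's syndrome)
- "ALT or AST >3x ULN with the appearance of fatigue, nausea, vomiting, right upper quadrant pain or tenderness" (the list continues with fever, rash and eosinophilia)

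**Monitoring.** In Protocol 8.2.6 the close-monitoring and comprehensive-evaluation tables also pair ALT with AST. If baseline is below 1.5x ULN, the triggers are multiples of ULN. If baseline is 1.5x ULN or more, they are multiples of the participant's own baseline. The third table, for the hepatic safety CRF, uses ALT, bilirubin and ALP without AST.

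**Phase 1.** Protocol 2.2 reports: "After single doses, transient elevations of liver enzymes (AST or ALT >2x ULN) and/or creatine kinase (>5x ULN) were observed". These elevations came without clinical signs or symptoms. Protocol 2.3.1 names hepatobiliary events as a potential risk.

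**The concern.** The protocol treats the two transaminases as a pair when it decides whether to stop dosing and when to repeat tests, but limits only one of them at entry. Two things follow.

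First, the numeric rules allow a first dose at an AST value that, on study, would call for interrupting or discontinuing intervention.

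Second, the baseline-relative triggers in 8.2.6 keep their place below the stopping limit only if baseline is bounded. For ALT, criterion 32 supplies the bound. For AST nothing does.

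At stake are the safety of the first dose in a rare participant and the order in which AST monitoring escalates. The efficacy conclusions are not involved.

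**Working it through.** The plan gives no figure to reproduce here. The check is a reading of the rules plus simple arithmetic in multiples of ULN.

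**Step 1. Which stopping conditions can one isolated screening AST meet?**

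| 7.1.1 condition | Met by one isolated AST value? |
|---|---|
| above 8x | Yes |
| above 5x for more than 2 weeks | No, needs duration |
| above 3x with bilirubin above 2x or INR above 1.5 | No, needs a second abnormal test; criterion 32 already excludes most raised bilirubin |
| above 3x with symptoms or eosinophilia | No, needs a second finding |

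So only the 8x condition matters for an isolated value.

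**Step 2. Inputs for the monitoring triggers.**

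- ALT entry limit: 3.0x ULN (criterion 32). AST entry limit: none.
- Repeat-test trigger for baseline *b* of 1.5x ULN or more: 2*b* (8.2.6, close monitoring).
- Comprehensive evaluation without symptoms, same baseline range: 3*b* (8.2.6).
- Single-value stop: 8x ULN (7.1.1).

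Two assumptions: each enzyme is compared with its own baseline, and baseline is no higher than the screening value. Protocol 9.3.1 defines baseline as the last measurement before the first dose, so a rise between Visit 1 and Visit 2 would lift the ALT figures too.

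**Step 3. Where does the repeat-test trigger cross the stop?**

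2*b* > 8 when *b* > 4.

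| Baseline *b* (x ULN) | Repeat test at 2*b* | Evaluation at 3*b* | Possible under criterion 32? |
|---|---|---|---|
| 1.5 | 3 | 4.5 | ALT and AST |
| 3 | 6 | 9 | ALT (its maximum) and AST |
| 4 | 8 | 12 | AST only |
| 6 | 12 | 18 | AST only |
| 8 | 16 | 24 | AST only |

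For ALT the repeat-test trigger is at most 2 × 3 = 6x ULN, which is 2x ULN below the stop. For AST above 4x ULN at entry it exceeds the stop.

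The comprehensive-evaluation column separates the two enzymes less cleanly. 3*b* > 8 when *b* > 2.67, so even ALT close to its limit passes 8x there (9x at *b* = 3). The argument therefore rests on the repeat-test trigger.

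**Step 4. After the change.** With AST also capped at 3.0x ULN, its repeat-test trigger is at most 6x ULN, the same as for ALT.

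**The case against.** The strongest reply is that the protocol already handles this participant. Results must be reviewed and the review documented (8.2.5), criteria are reconfirmed before the first dose (1.3), criteria 18 and 50 allow exclusion on opinion, and criterion 26 excludes active severe liver disease. An AST above 8x ULN would rarely pass all of that. This stands as a reason why cases should be few. It does not explain the asymmetry, because the same safeguards exist for ALT, ALP and bilirubin, and those were still given numbers.

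A second reply is that 8.2.6 foresees a raised baseline and manages it relative to baseline. That is true, but Step 3 shows that this is where an unbounded baseline causes trouble.

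A third is that the absolute limits remain. This also stands. Chemistry is drawn at every visit, and an AST that stays above 5x for more than 2 weeks meets a stopping condition whatever the baseline. What is lost is the earlier repeat-test signal, not the stop.

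A fourth is that leaving AST out may be deliberate. The hepatic CRF triggers use the same three analytes, and isolated AST can come from muscle in a population that is all on statins (criterion 4). That is possible, but no rationale is given.

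A reader might go further in three ways that the documents do not support:

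- *That 5.2 and 7.1.1 contradict each other.* 7.1.1 is worded for conditions arising on study and is silent on pre-dose values. This is a gap.
- *That AST appearing in every transaminase stopping rule and in no entry criterion measures the size of the problem.* Only one of those rules can be met by an isolated screening value, and most entry criteria have nothing to do with liver tests.
- *That the effect lasting to Day 169 in Phase 1 means lasting liver exposure to harm.* That statement in 2.2 concerns ANGPTL3, triglycerides and LDL-C. The liver enzyme elevations there were transient.

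**Conclusion.** The point holds as a minor gap. Criterion 32 leaves AST without a numeric limit, so first-dose exclusion for a high AST depends on judgment, and for AST above 4x ULN at entry the repeat-test trigger in 8.2.6 lies above the 8x stopping limit.

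The documents give no frequency for such cases; they are probably rare and no probability is claimed. The stated power (above 99%) and the primary ApoB analysis are unaffected. The conclusion assumes the enzyme-by-enzyme reading of 8.2.6 and the baseline assumption given in the working.

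**What to change.** Amend the first line of criterion 32 to: *ALT or AST >3.0X ULN*. It applies to the AST already drawn at Visit 1, so it needs no new test or visit.

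The cost is a few more screen failures, including some participants with AST of muscle origin. CK is in the same panel and helps to recognise these. The single retest in 5.4 offsets the loss only in part, because it is reserved for results that the investigator attributes to error or extenuating circumstances, and a genuine muscle-origin value may not qualify. By Step 3, any AST limit up to 4x ULN would keep the repeat-test trigger from exceeding the stop; 3.0x is proposed because it matches ALT.

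The change governs the screening value only. Visit 1 is about 45 days before randomization, and a longer screening period is not a deviation (1.3), so AST on the day of dosing is not guaranteed. If enrolment has already closed, listing participants with baseline AST above 3x ULN beside the hepatic tables in SAP 4.6.7.1.3 would at least show whether the gap was ever used.
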